Given these aims, we modeled a sequential design with maximum *N* where the data collection continues until either the threshold for compelling evidence is met or the maximum *N* is reached. Initially, forty-one labs indicated interest in the project, we expect to have up to 30 data-collecting labs. Each lab was expected to collect data of at least N = 70 participants, with a stopping *N* at 120 (translating to *Min* = 420 and *Max* = 720 participants per condition). We intended to be able to detect an effect size of *d* = 0.20; here we modeled the true value to vary between labs by repeatedly (for each simulation) drawing from a normal distribution, $\delta \sim N(0.20, 0.05)$, with a 95% probability that the effect size falls between *d* = 0.10 and 0.30.

The present study aimed at testing the effectiveness of four stand-alone interventions using a between-subjects adaptive group design, where upon hitting a threshold of compelling evidence in one condition, the plan was to allocate the rest of the participants into other conditions where this has not been the case yet. The design analysis, however, assumed a conservative scenario with equal *N* across all conditions, therefore, simplifying the computations to a single between-subjects *t*-test scenario.

The results (see Figure 1) show that, given the assumed design, the probability of the test to arrive at the boundary of compelling evidence (BF = 10 or 1/10) was .79 (.72 at H_1 and .07 erroneously at H_0). The probability of terminating at maximum N of 720 per condition was .21; .05 of showing some evidence for H_1 (BF > 3), .13 of being inconclusive (3 > BF > 1/3), and .03 of showing evidence for H_0 (BF < 1/3). For the test of a single condition against controls, the sequential design is expected to be 27% more effective than collecting a fixed

maximum N per lab, with the average N at stopping point (*BF* boundary and maximum N) at 526. Even conservatively assuming a balanced-N situation, the informativeness of the design thus appears to be adequate and the use of adaptive design is likely to further enhance informativeness and/or resource efficiency. Figure 1 shows the results of the simulation of the sequential design with 10000 iterations.

Figure 1. Design analysis for the sequential bayesian design with maximum N

Procedure

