We implemented the sequential design as being adaptive, stopping collecting the data for a given test of a condition after obtaining a Bayes Factor of 10 in favor of H_1 or a Bayes factor of 1/10 in favor of $H_{0.}$, and re-assigning the remaining participants into other conditions, where such a threshold has not been met. We chose a Bayes Factor of 10, because according to the classification of Lee and Wagenmakers (2013), it demarcates the threshold between moderate and strong evidence. We started monitoring the Bayes Factor when there were at least 100 participants in each group. We chose 100 arbitrarily, because with a smaller sample size, the probability of misleading evidence (i.e., a Bayes Factor trajectory that arrives at the "wrong" boundary, that is, at the H_0 boundary when H_1 is correct and the other way around) would have been higher. Here, using a sample size of 100 and a Bayes Factor of 10 we aimed to substantially decrease the probability of misleading evidence (Stefan et al., 2017).

We monitored the Bayes Factor and recorded the interim analysis every 3 days to check whether the threshold was reached⁷. If the threshold was not reached (BF of 10 or of 1/10) we stopped the data collection after that the maximum number of participants⁸ was reached. If for any of the four tests, one of these three conditions was not met (i.e., BF of 10 in favor of H₁; BF of 1/10 in favor of H₀; the maximum number of participants is reached), the data collection was terminated four months after the start of the experiment. When one of these three conditions has been met, we stopped allocating participants to that particular experimental condition and we allocated them to the remaining conditions for which this has not been the case yet. If the data collection ends before all the sites are able to collect at least 70 participants⁹ (because we would have reached a Bayes Factor of 10 in favor of H₁ or of 1/10 in favor of H₀ for a given test of a condition), we will continue with the data collection by reopening all groups and equitably allocating each participant to each group until each site would have collected at least 70 participants. In this case, we would use this sample for exploratory analyses.

Exploratory analyses

We also carried out analyses exploring the effect of experimental conditions on pleasure, arousal, and dominance, and for the potential moderating effect of neuroticism. We

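### The design analysis figures for ending wrongly at H0 (.07), ending at maximum N (.21) and average stopping N (526) do not describe the planned monitoring from 100 per group every 3 days

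*Combined protocol and SAP*

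**What the plan says.** All references are to the combined protocol and SAP.

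- **Bayesian design analysis.** The section names the likelihood of convincing but misleading evidence as its second aim. It models a sequential design with a maximum N, 30 labs and 70 to 120 participants per lab, "translating to *Min* = 420 and *Max* = 720 participants per condition". The true effect is drawn from N(0.20, 0.05) in each simulation. The probability of reaching a boundary "was .79 (.72 at H_1 and .07 erroneously at H_0"). The remaining .21 end at 720 per condition, split .05 / .13 / .03 (some evidence for H1, inconclusive, evidence for H0). The sequential design is put at 27% more effective than a fixed maximum, "with the average N at stopping point (*BF* boundary and maximum N) at 526". The section declares two simplifications, equal N and a single t-test. It does not state the simulated first look, the spacing of looks or the r-scale. It does give the size of the run: "Figure 1 shows the results of the simulation of the sequential design with 10000 iterations".
- **Confirmatory analyses.** The r-scale for the tests is √2/2. "We started monitoring the Bayes Factor when there were at least 100 participants in each group". "We monitored the Bayes Factor and recorded the interim analysis every 3 days". If no stopping condition is met, "the data collection was terminated four months after the start of the experiment". If collection ends before every site has 70 participants, "we will continue with the data collection by reopening all groups and equitably allocating each participant to each group", and that sample is for exploratory analyses. A confirmatory stop below 420 per condition is therefore part of the plan.

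**The concern.** The reported sums are correct: .72 + .07 = .79, .79 + .21 = 1, .05 + .13 + .03 = .21 and 1 − 526/720 = .27. The question is which monitoring rule they belong to. A rule that can stop from 100 per group should stop earlier on average, and has more chances to cross a boundary in the wrong direction, than one that first looks later. No section gives operating characteristics for the rule that starts at 100. If the stated figures come from another look schedule, the misleading-evidence rate that the section set out to establish is understated, and 526 is not the expected N at the confirmatory stop.

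**Working it through.** **Inputs.** From Bayesian design analysis: δ ~ N(0.20, 0.05), one draw per run; equal N; one two-sample comparison; maximum 720 per condition (120 × 30 / 5); minimum 420 (70 × 30 / 5). From Confirmatory analyses: two-sided JZS test with r = √2/2; boundaries 10 and 1/10; first look at 100 per group; looks every 3 days; four-month limit.

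**Spacing (assumption).** Four months is about 122 days, or 122/3 = 40.7 looks. With 720 per group spread evenly, 720/40.7 = 17.7, so about 18 per group between looks.

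**Bayes factor.** With n per group and ν = 2n − 2, BF10 = ∫ (1 + ng/2)^(−1/2) · [1 + t²/((1 + ng/2)ν)]^(−(ν+1)/2) · p(g) dg ÷ [1 + t²/ν]^(−(ν+1)/2), where g ~ inverse-gamma(1/2, r²/2). A run stops at the first look with BF10 ≥ 10 or ≤ 1/10. At 420 per group these are |t| ≥ 3.154 and |t| ≤ 0.727; at 720, |t| ≥ 3.225 and |t| ≤ 1.03. Even at t = 0, BF10 ≤ 1/10 cannot occur below 247 per group.

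**Results** (60,000 simulated paths, true effect as above):

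| First look | Step per group | At H1 | Wrongly at H0 | At max N | Average N at stop |
|---|---|---|---|---|---|
| Plan's stated figures | not given | .72 | .07 | .21 | 526 |
| 420 | 10 | .722 | .065 | .213 | 523 |
| 420 | 18 | .717 | .063 | .220 | 527 |
| 100 | 10 | .732 | .097 | .171 | 393 |
| 100 | 18 | .727 | .092 | .181 | 405 |
| 100 | 50 | .715 | .080 | .205 | 433 |
| 100 | 75 | .710 | .073 | .217 | 450 |
| 100 | 100 | .705 | .070 | .225 | 464 |

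Independent repeats agree to within simulation error; at step 50 the average N ran up to about 437.

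**Reproducing the plan.** A first look at 420 with step 10 also gives the stated split at maximum N (.05 / .13 / .03), so all the reported figures are closely matched. From 100 with step 18 the split is .05 / .11 / .02.

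**Where the difference arises.** With a start at 100 and step 18, .568 of runs stop before 420 per group: .494 at H1 and .074 wrongly at H0.

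**Simulation noise.** The standard error of .07 at 10,000 iterations is √(.07 × .93 / 10,000) = .0026, so .07 against .09 is not noise.

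**Accrual pace.** With 3-day looks and four-month accrual in even, staggered, front-loaded or back-loaded form, wrong H0 is .092 to .095 and average N 407 to 416. If recruitment finishes in 60 days, these are .084 to .087 and 425 to 432. If it finishes in 29 to 36 days, they are .076 to .078 and 446 to 457.

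**No true effect.** BF10 ≥ 10 is reached in about .015 of tests from a start at 100 (step 18), against about .006 from a start at 420.

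**The case against.** **The first look at 420 is not stated.** This stands. The figure and code could not be examined, so 420 is inferred from the stated minimum and the close match. A reader might conclude that the simulation certainly began at 420; the documents do not establish that. One other reading comes close: a start at 100 with steps of 60 to 75, counting N as never below 420, averages 524 to 529. That spacing needs all 720 per group within 720/60 × 3 = 36 to 720/75 × 3 = 29 days, and the section defines its average as N at the stopping point.

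**The r-scale is borrowed.** The design analysis does not state it; √2/2 comes from Confirmatory analyses. The choice matters: from 100 with step 18, wrong H0 is about .02 at r = .5 and .25 at r = 1.

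**The recomputed figures are not those of the adaptive trial.** This also stands. The plan reallocates participants from stopped arms and shares one control. A rough simulation of that (four arms plus control, 3,600 in total, 90 per look, independent effects, known variance, 5,000 trials) gave .82 at H1, .09 wrongly at H0, .09 unresolved and a mean stopping N near 456 per mindfulness arm. Only the wrong-H0 rate carries over. But both sides of the comparison above keep the declared simplifications, so these cannot explain the gap.

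**The plan disclaims error-rate control.** It does, but it chose to report the misleading-evidence rate, and that rate should belong to the rule used.

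**The effect is small.** For the error rate, yes. At coarse spacing wrong H0 falls to about .08, and the maximum-N probability at step 50 (.205) agrees with the stated .21. The average N does not close: steps of 1 to 100 gave 373 to 464. Steps wide enough to approach 526 lose the match elsewhere (step 200: N 509, wrong H0 .060, H1 .697; step 310: N 555, wrong H0 .049).

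**Conclusion.** The concern holds as a modest reporting correction. The stated .07, .21 and 526 do not describe looks every 3 days from 100 per group. Under equal N, a single t-test, r = √2/2 and about 18 per group per look, the matching values are about .09, .18 and 405. For 10 to 50 per look, wrong H0 is about .10 to .08 and average N about 393 to 437. The average N is the firmest part; the shift in the error rate depends on accrual pace.

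Two stronger readings are not supported. A reader might infer that the design is inadequate, but the probability of ending at H1 (.73 against .72) and the conclusion on informativeness are essentially unchanged. A reader might also infer that the 27% efficiency figure is wrong, or that the fall from 720 to about 405 is a larger saving. The reopening rule can bring in participants after the confirmatory stop, so N at that stop is not the number collected. Nor can the number collected be had by raising each arm to 420, because reopening is triggered for the trial as a whole.

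**What to change.** Rerun the design analysis with the first look at 100 per group and the accrual expected per 3-day interval. In the Bayesian design analysis section:

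- State the simulated first look, the spacing, the r-scale and the accrual pace.
- Replace the boundary and maximum-N probabilities and the average N.
- Report misleading-evidence rates under both H1 and H0.
- Label the results as equal-N, single-comparison figures that leave out adaptive reallocation and the shared control.
- Report N at the confirmatory stop separately from participants collected, and do not present 720 to about 405 as a resource saving.

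Wording to adapt once rerun: Under equal N and a single comparison (r = √2/2, first look at 100 per group, about 18 per group between looks), a boundary was reached with probability about .82 (.73 at H1, .09 erroneously at H0) and .18 ended at 720 per condition. Average N at the confirmatory stop was about 405. With no true effect, BF10 ≥ 10 was reached in about .015 of tests. Adaptive reallocation and the shared control were not modelled.

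The cost is one simulation and a few replaced figures. Thresholds, start of monitoring and maximum N need no change.

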To assess whether any of the chosen mindfulness exercises were more effective than the randomly sampled control conditions to reduce stress in participants, we planned to conduct a sequential design. We sampled participants until a Bayes Factor threshold for compelling evidence was met or until a maximally feasible number of participants was collected (Schönbrodt et al., 2017). Unlike in the frequentist approach, the aim of this procedure was not the control of error rates, but to gauge the relative support provided by the present data in favor of one of two competing hypotheses, H_1 and H_0 . In the frequentist approach, the practice of adjusting the sampling plan after peeking at the data would have increased the Type 1 error rate, but in the Bayesian approach, the data collection could be stopped anytime without having any consequences on the interpretation of the Bayes Factor (Rouder, 2014). We divided our analysis workflow into confirmatory and exploratory. The sequential testing was tied to the confirmatory analysis phase while the exploratory analyses had no role in the decisions related to sampling.

Confirmatory analyses

As the aim of the present study was to assess the effectiveness of four stand-alone mindfulness interventions without any aspirations to draw broad inferences about mindfulness intervention in general, we planned to carry out four independent comparisons with the active controls. Therefore, we carried out four independent-samples Bayesian t-tests to determine whether there was a difference between each mindfulness exercise and the active control condition. We employed a two-tailed test using a non-informative JZS Cauchy prior for the alternative hypothesis with a default *r*-scale of $\sqrt{2}/2$ (Rouder, Speckman, Sun, Morey, & Iverson 2009). To account for the hierarchical nature of the data, we compared the condition means using a Bayesian mixed-effects model that involved a random intercept for lab and for different stories used in the non-mindful active control condition.

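### The design-analysis figures describe a plain t-test first looked at from about 420 per condition, not the planned monitoring from 100 per group, and they leave out the story term that the plan may use

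*Combined protocol and SAP*

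**What the plan says.** The Bayesian design analysis section sets three aims. The second is to find how often strong evidence would point the wrong way. With 30 labs collecting 70 to 120 participants each, it gives sample sizes "translating to *Min* = 420 and *Max* = 720 participants per condition". "The design analysis, however, assumed a conservative scenario with equal" *N* in all conditions, "therefore, simplifying the computations to a single between-subjects" *t*-test. The true effect is drawn from N(0.20, 0.05). The reported results are .79 for reaching a boundary (.72 at H1, .07 wrongly at H0) and .21 for ending at 720 per condition (.05, .13 and .03 for some evidence for H1, inconclusive, and evidence for H0). The section says "the sequential design is expected to be 27% more effective" than a fixed maximum, "with the average N at stopping point" given as 526. Its conclusion is "Even conservatively assuming a balanced-N situation, the informativeness of the design thus appears to be adequate".

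The Confirmatory analyses section plans four independent-samples Bayesian t-tests, two-tailed, with a "non-informative JZS Cauchy prior for the alternative hypothesis" of scale √2/2. It then says that condition means are compared using a "Bayesian mixed-effects model that involved a random intercept for lab and for different stories used in the non-mindful active control condition". Monitoring starts at 100 per group and repeats every 3 days for up to four months. Participants are reassigned once a comparison has stopped. The same section describes misleading evidence in both directions.

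The Procedure section gives each control participant one of three stories with equal probability. The text states no story SD, no prior for story variance and no story code for mindfulness participants. The Materials section points to a code repository, which may contain the last two.

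**The concern.** The design figures support the claim of adequate informativeness, so they should describe the rule that will stop each comparison. They differ from it in up to two ways: the first look, and possibly the model.

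The story term is the more serious of the two. Story has three levels and exists only in the control arm. A story variance g therefore adds g/3 to the variance of every mindfulness-versus-control contrast, and further recruitment does not reduce that part. Equal N may well be a conservative assumption, but leaving out story is not.

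The design analysis text also reports only a scenario with a true effect. It therefore does not say how often an exercise with no effect would reach the H1 boundary, although the second aim covers that error. These Bayes factors decide when an arm closes and where later participants go, so a reader needs both rates.

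**Working it through.** **Inputs from the plan.** Boundaries 10 and 1/10; Cauchy scale √2/2; two-sided; effect ~ N(0.20, 0.05); minimum 70 × 30 / 5 = 420 and maximum 120 × 30 / 5 = 720 per condition; planned first look 100; about 120 / 3 = 40 looks in four months. **Assumed:** residual SD 1; one effect draw per simulated trial (one draw per lab gave about .78 and .03, which does not match the stated .72 and .07); on average a third of controls per story.

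**Step 1. Plain t-test.** With ν = 2n − 2 and g ~ inverse-gamma(1/2, 0.5/2), BF10 is the mean over g of (1 + ng/2)^(−1/2) · (1 + t²/((1 + ng/2)ν))^(−(ν+1)/2), divided by (1 + t²/ν)^(−(ν+1)/2).

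| | H1 | wrong H0 | either | average n | saving |
|---|---|---|---|---|---|
| Stated | .72 | .07 | .79 | 526 | 1 − 526/720 = 27% |
| From 420, step 10 | .72 | .067 | .79 | 523 | 1 − 523/720 = 27% |
| From 100, 40 looks | .725 | .095 | .82 | 404 | 1 − 404/720 = 44% |

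From 420, the split at maximum N also matches (.05/.13/.03), and steps of 12 to 18 give average n 525 to 527. No start at 200 or earlier comes near 526: average n was 359 to 453 at every step tried. From 100 with a step of 18 (720/40) the result is .73/.093/.82 with average n 406, so the look spacing matters little.

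**Step 2. If the mixed model supplies the Bayes factor.** As an illustration, treat the story SD s as known. The contrast variance is 2/n + s²/3, and the effective n is 2/(2/n + s²/3). At s = .10 and n = 720 this is 2/(.00278 + .00333) = 327. First look at 100, step 18:

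| s (assumed) | effective n at 720 | H1 | wrong H0 | either | average n |
|---|---|---|---|---|---|
| 0 | 720 | .73 | .09 | .82 | 406 |
| .05 | 554 | .63 | .09 | .72 | 446 |
| .10 | 327 | .42 | .07 | .49 | 535 |
| .15 | 195 | .25 | 0 | .25 | 612 |
| .20 | 124 | .15 | 0 | .15 | 651 |

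The 1/10 boundary needs an effective n of about 247. At s of about .15 or more it is out of reach up to 720 per condition.

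The prior and coding matter as much as s. A full mixed model was simulated with unknown residual variance, 30 labs with lab SD .2 (assumed) and no true story variation (2,000 trials, Monte Carlo SE about .01). With no story term P(BF10 ≥ 10) is .72, so the lab intercept does not drive the loss. With a half-normal prior of scale .02, .05 or .1 on the story SD it is .71, .64 or .44 when story is coded in controls only. It is .66, .34 or .05 when the mindfulness recording counts as a fourth level, because the added variance is then 4g/3.

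**Step 3. If a t-test that ignores story supplies it.** Rate of reaching the H1 boundary when the true effect is zero:

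| s (assumed) | 0 | .05 | .10 | .20 |
|---|---|---|---|---|
| From 420 | .005 | .010 | .048 | .213 |
| From 100 | about .015 | about .025 | about .06 | about .24 |

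**The case against.** The t-test simplification is disclosed, and the results are offered for the assumed design. That stands, but the disclosure covers equal N and a t-test. It does not mention the different first look or the missing story term.

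A reader might infer that starting at 100 harms the design. It mostly helps: the H1 probability hardly moves, boundary arrival rises and average n falls. The cost is the 2 to 3 points of extra wrong stops for the null.

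The simulations in the working cap each arm at 720, whereas the plan reassigns participants and footnote 8 caps only the total. A plain t-test simulation with four arms, a shared control, a total of 3,600 and a first look at 100 gave .72/.09/.81 without reassignment and .81/.10/.91 with it. Equal N is therefore conservative for boundary arrival, as the plan says. This does not address story.

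A reader might also infer that the mixed model certainly drives stopping, or that the story term removes any chance of reaching 10. The documents support neither. The Confirmatory analyses section names both kinds of test. A near-zero chance arises if the scale √2/2 is carried over to story variance, but the plan states that prior for the alternative hypothesis only.

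The stories were chosen to be alike, so the story SD may be small; no figure is given, so it cannot be bounded. Figure 1 could not be seen and may show a null scenario. The plan also says that control of error rates is not its aim, yet it lists misleading evidence among the things to be established.

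**Conclusion.** The point holds in this form. The stated .07, .79, 526 and 27% do not describe monitoring from 100 per group. For the same plain t-test they become about .09, .82, 405 and 44%, while .72 stays at about .73. This part needs no assumption about story.

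The story part is certain in direction only. If the mixed model drives stopping, the chance of reaching 10 is lower than for the plain t-test. The loss ranges from almost nothing to most of it, depending on a story SD, prior and coding that the text does not give. If a t-test ignoring story drives stopping, the wrong-H1 rate under a true null rises from about .015 to about .24 as the assumed story SD goes from 0 to .20. These are ranges, not predictions. They rest on residual SD 1, a cap of 720 per arm and no reassignment.

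The design should not be called inadequate on this evidence. What can be said is that the reported figures do not show whether it is adequate.

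**What to change.** 1. In the Confirmatory analyses section, state which model supplies the monitored Bayes factor. If story enters it, give the story coding and the story-variance prior (copied from the repository if they are there), fixed before the first look. Whether story is random or fixed is for the investigators to choose.
2. Rerun the design simulation with that model, the start at 100 per group and looks every 3 days. Include reassignment, or say that it is left out.
3. Restate .72, .07, .79, 526 and 27%.
4. Report the wrong-H1 rate under a true null over a stated range of story SD, for example 0 to .20, unless Figure 1 already shows it.
5. Limit the word *conservatively* to the equal-N assumption.

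The cost is a few sentences and some new simulation work. Repeating a mixed-model Bayes factor over about 40 looks and several scenarios is more than a rerun of the existing t-test code. No extra participants are needed. The restated figures may be less favourable, and the claim of adequacy may then have to be softened.
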